In order to collect additional organizational metrics, a key informant interview and survey will be conducted with state program managers. These will be performed for all 24 states at three time points- baseline and in June during years 2 and 3. This will help in evaluating the impact of the training intervention on the capacity for sustainability and institutionalization of the TC program within the organization.

Step 1: Identifying relevant measures. Relevant state-level sustainability metrics will be identified within the 24 selected states from various sources, including CDC Best Practices, ALA State of Tobacco Control, empirical literature, and consultation of our advisory group.

Step 2: Key Informant Interview and Survey. TC program managers will be contacted to complete a phone interview and survey. The interview and survey will only collect organizational metrics not collected in reporting records, and no personal information will be collected. We will record phone interviews to ensure comprehensive analysis by trained abstracters. Prior to the interview, program managers will be provided a copy of the questions to be asked from a standard script created by the research team. Each question is formatted in multiple choice, e.g., “How long has the program been in existence?” [1: Less than 1 year; 2: 1-3 years; 3: 3-5 years; 4: 5-10 years; 5: 10 or more years; 6: Don’t know]. Using this method, program managers will provide unambiguous answers to data points not collected by record abstraction.

Step 3: Establishing reliability and validity. Data collected via interview/survey and abstraction are subject to bias that may result from rater subjectivity.¹⁰⁴ In order to determine the agreement between the two evaluators, a baseline reliability evaluation will be conducted early in the process to calculate inter-rater reliability. In order to determine validity of self-reported data from the PSAT, agreement between self-reported, record-based information, and interview/survey information will be assessed. Both inter-rater reliability and validity of self-reported data will be checked at baseline and two other time points.

Phase 3 (Aim 3):

C.7. (Aim 3): Actively disseminate The Program Sustainability Action Planning Model and Training Curriculum materials and study results to support future adoption.

[figure not shown]
No treatment with intervention or comparison groups will take place during this phase.

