10.0 Recordkeeping

The Principal Investigator, [name], will be responsible for monitoring the data safety and quality of the overall study. This is a minimal risk study that does not warrant a formal Data Safety Monitoring Board.

Program Sustainability Assessment Tool (PSAT). The PSAT is a 40-item measure of a program's sustainability capacity which requires 10-15 minutes to complete. Individuals selected by state TC program managers will be invited to complete the PSAT online via our secure website <https://sustaintool.org/>. Data collected through the website is automatically de-identified by the website and aggregated at the state level. E-mail addresses are collected on the site, but solely for website management, technical assistance, and user access. See Appendix A for full copy.

Workshop Data Collection Form. Several process measures will be collected to assess the effectiveness of the training and support delivered. All measures will be collected via survey at the completion of each training component or tracked by review of programmatic records (i.e., action plan, meeting minutes). Quantitative data collected for this aim will be analyzed using descriptive statistics. Qualitative analysis of programmatic records will be conducted following procedures outlined. See Appendix B for full copy.

Dosage delivered is the number of units of an intervention delivered or provided.¹⁰¹ For this study, this measure will be defined by the number of hours of training and technical assistance provided to each state.

Dosage received is the extent to which participants engage with or use the materials provided.¹⁰¹ This will be measured by whether or not the action plan is completed and implemented, whether the workgroup utilizes the resources and materials provided, and the extent to which the action plan is implemented.

Participant reactions will be measured by the extent to which the participants felt that the objectives of the training and technical assistance were achieved, satisfaction with the training and technical assistance and perceived usefulness of the training provided.

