Appendix B. Data Collection Form for Workshop

I. DOSAGE DELIVERED:

number of units of an intervention delivered or provided

1. # Stakeholders to complete PSAT
2. # Stakeholders to attend training
3. # Stakeholders to attend TA calls
4. # hours of training
5. # hours of TA

II. DOSAGE RECEIVED:

extent to which participants engage with or use materials or recommended resources.

Service-Related Questions related to Comprehension- required for properly completing tools

1. After viewing the Introduction to Sustainability Webinar, I now understand the concept of program sustainability completely (5 point Likert scale strongly agree- strongly disagree).
2. After attending/viewing the Action Planning Workshop, I now understand the process of Program Sustainability Action Planning completely (5 point Likert scale strongly agree- strongly disagree).
3. The handouts provided helped me to understand the Action Planning Workshop material (5 point Likert scale strongly agree- strongly disagree).

Action Plan Implementation-Related Questions (Implementation- “measures the extent to which users engaged with or used”)

1. My program created a program sustainability action plan based on the results of the Program Sustainability Assessment Tool and Action Planning Training (Y/N).
2. My program implemented the activities outlined in our program sustainability Action Plan (Y/N).
3. Please indicate the percentage of your sustainability plan your program has implemented (i.e., If you met 3 out 4 objectives, you would select 75%).

_____ 10% or less _____ 25% _____ 50% _____ 75% _____ 90% or more

4. Please estimate the amount of time per month your sustainability plan was discussed among staff.

_____ Less than 1 hour per month _____ 1-3 hours _____ 3-5 hours _____ 5-7 hours _____ 7-9 hours _____ 10+

5. Please estimate the amount of time per month your program staff focused on implementing your sustainability plan steps.

Less than 1 hour per month 1-3 hours 3-5 hours 5-7 hours 7-9 hours 10+

III. PARTICIPANT REACTION

Service Delivery: PSAT and Report-Related Questions (Relevance, Satisfaction)

1. I found the Program Sustainability Assessment Tool to be informative (5 point Likert scale strongly agree- strongly disagree).
2. The Program Sustainability Assessment Tool and Report helped me to think about program sustainability in ways I hadn't considered before (5 point Likert scale strongly agree- strongly disagree).

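### Appendix B, Dosage received: the plan-implementation and time scales leave some possible answers with no box and others with two, which coarsens the only graded survey measure of implementation (minor)

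*Combined protocol and SAP*

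**What the plan says.** Appendix B (Data Collection Form for Workshop), part II, item 3 reads: "Please indicate the percentage of your sustainability plan your program has implemented (i.e., If you met 3 out 4 objectives, you would select 75" per cent. The options are "10% or less _____ 25% _____ 50% _____ 75% _____ 90% or more". These are three single points and two open ends. There is no rounding instruction, and 0% and 100% have no boxes of their own.

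Item 2, just before it, is a yes/no question: "My program implemented the activities outlined in our program sustainability Action Plan (Y/N"). Item 1 is also yes/no and asks whether a plan was created.

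Items 4 and 5 ask for estimates of monthly time spent discussing the plan and carrying out its steps. Both use the boxes "Less than 1 hour per month _____ 1-3 hours _____ 3-5 hours _____ 5-7 hours _____ 7-9 hours _____ 10", the last printed with a plus sign.

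Section 10.0 (Recordkeeping) defines dosage received to include "the extent to which the action plan is implemented". Section 9.0, C.6.e, uses the dose measures to calculate rates of adoption and implementation. Equation 1 in the same section has a dose term D and a group-by-dose interaction, and the text says the analysis controls for differing dosage reception and delivery. How D is built from the form is not stated.

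On a separate matter, the example question on program age in section 5.1 (Key Informant Interview and Survey, Step 2) offers "2: 1-3 years; 3: 3-5 years; 4: 5-10 years; 5: 10 or more years". The section describes such answers as free of ambiguity.

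**The concern.** Item 3 tells the respondent to work out a fraction and tick the matching percentage. If the fraction is not on the list, the respondent must choose a neighbouring value, and the form does not say which. The true numerator and denominator are not recorded, so the form itself cannot correct the choice later. In items 4 and 5, adjacent boxes share endpoints and the last two do not meet.

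Item 3 is the form's only graded measure of how much of the plan was implemented: item 2 has no partial option, and items 4 and 5 grade time rather than completion. With 12 intervention states, a few answers pushed to a neighbouring box can visibly move a reported implementation rate. They could also move a dose variable, if one is built from these items.

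**Working it through.** **Inputs.** Item 3 boxes: ≤10, 25, 50, 75, ≥90 (Appendix B). Rule: objectives met ÷ objectives in the plan, from the worked example "If you met 3 out 4 objectives, you would select 75" per cent. Time boxes: <1, 1–3, 3–5, 5–7, 7–9, 10+ hours per month, endpoints included as printed. Number of objectives per plan, n: not given in the protocol, so I assume n = 1 to 12 and show the whole range.

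**The form's own figure.** 3/4 = 75%, which has a box. The example works.

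**Item 3.** For each n, list 100·k/n for k = 0, …, n. A result has a box if it is ≤10, equal to 25, 50 or 75, or ≥90. For a result with no box, the distance is the smallest gap to a printed label (10, 25, 50, 75, 90).

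| n | Results with no box | Largest distance to nearest label (points) |
|---|---|---|
| 1 | 0 of 2 | 0 |
| 2 | 0 of 3 | 0 |
| 3 | 2 of 4 (33.3, 66.7%) | 8.3 |
| 4 | 0 of 5 | 0 |
| 5 | 4 of 6 (20, 40, 60, 80%) | 10.0 |
| 6 | 4 of 7 (16.7, 33.3, 66.7, 83.3%) | 8.3 |
| 7 | 6 of 8 | 7.1 |
| 8 | 4 of 9 (12.5, 37.5, 62.5, 87.5%) | 12.5 |
| 9 | 8 of 10 | 8.3 |
| 10 | 6 of 11 | 10.0 |
| 11 | 8 of 12 | 11.4 |
| 12 | 6 of 13 | 8.3 |

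Only n = 1, 2 and 4 fit in full. In the affected sizes the largest distance runs from 7.1 to 12.5 points.

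**Ties.** 3/8 = 37.5%, and 37.5 − 25 = 50 − 37.5 = 12.5. Likewise 62.5 − 50 = 75 − 62.5 = 12.5. Two eight-objective states with three met could be recorded at 25% and 50%, which is 25 points apart. These are the only exact ties for n up to 12.

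**The ends of the scale.** On item 3 alone, 0% shares a box with anything up to 10%, and 100% with anything from 90%. The midpoint between the labels 10 and 25 is 17.5. Under nearest-label choice, one objective met out of five (20%) goes to 25%, but one out of six (16.7%) joins zero in the lowest box. By symmetry, five of six (83.3%) lies above the midpoint 82.5 and joins full completion.

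**Items 4 and 5.**

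| Hours per month | Boxes that fit |
|---|---|
| 3 | 1–3 and 3–5 |
| 5 | 3–5 and 5–7 |
| 7 | 5–7 and 7–9 |
| above 9 and below 10 (e.g. 9.5) | none |
| 0, 0.5, 1, 2, 4, 6, 8, 9, 10, 11 | exactly one |

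The same boxes are printed for both items, so this does not look like damage from text extraction.

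**Program-age example, section 5.1.** Answers of 3, 5 and 10 years each fit two options.

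**The case against.** The best reply is that these are approximate self-report items on a process form. Items 4 and 5 ask for estimates, and an ambiguous endpoint moves an answer by one adjacent box. A respondent who takes the nearest label on item 3 is at most 12.5 points out, and the choice is unique except at 3/8 and 5/8. That is fair and limits the size of the point. But the form does not tell respondents to take the nearest label.

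A reader might infer more than the documents support, in four ways.

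- **That zero implementation cannot be identified.** Items 1 and 2 partly separate it: a no on item 1 means no training-based plan exists, and a no on item 2 with the lowest box on item 3 points to little or nothing done. Section 10.0 also provides for review of programmatic records and lists plan implementation as an abstraction variable, and section 5.1 has quarterly plan review for trained states. The help is partial, because item 2 has no middle option and no scale is given for the abstracted variable.
- **That the scale is wrong for typical plans.** No plan size is stated, so nothing can be called typical.
- **That the outcome model is damaged.** The make-up of D is not given. Dosage delivered is counted in hours on separate items and is unaffected. The definition of dosage received in section 10.0 does not name discussion or staff time, so items 4 and 5 have no stated analytic role.
- **That the key informant question shows the same fault in the dose data.** It concerns program age, is a single example, and is asked in an interview where a boundary answer can be clarified.

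**Conclusion.** The structural fault stands; its consequence is minor. Item 3 has unmatched partial results for every plan size from 1 to 12 except 1, 2 and 4. Items 4 and 5 have three doubly classified whole-hour values and one gap. The effect is a coarser graded survey measure of implementation. That measure feeds dosage received and can feed the implementation rates. It reaches the dose terms in Equation 1 only if it is used to build D. The randomised comparison is otherwise unaffected.

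The conclusion rests on reading the boxes as printed and, for the 12.5-point bound, on respondents choosing the nearest label. Because neither plan sizes nor the construction of D is stated, the effect on any estimate cannot be quantified. The case for changing the form is that the gain in precision is nearly free.

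**What to change.** Replace item 3 with two numeric entries, the number of objectives in the plan and the number met to date (0 allowed), and compute the percentage centrally. No result is then unmatched for any plan size, and 0% and 100% are recorded as such.

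For items 4 and 5, ask for hours per month as a number, or use half-open bins: <1, 1 to <3, 3 to <5, 5 to <7, 7 to <10, 10 or more. No value then falls in two bins or in none.

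As a separate tidy-up, make the program-age options in section 5.1 non-overlapping: <1, 1 to <3, 3 to <5, 5 to <10, 10 or more years, keeping the don't-know option.

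The cost is an edit to the survey form and the interview script, with no extra respondents, visits or staff.
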